### Rationale for Biomarkers selection

**microRNA:** Modulation of biological markers after treatment and the correlation of these findings with modification of lung nodules diameters will be investigated as secondary endpoints. In particular, we have recently identified serum circulating microRNA (miRNA) able to accurately predict the presence of lung cancer during early stages disease. The test was accurate enough to capture the onset of the disease in patients of whom serum samples were available before and after diagnosis of lung cancer by ld-CT. The same signature was also able to identify the premalignant GGO lesions among Cosmos 1 participants (unpublished data). In brief, we screened a group of 27 individuals with GGO lung nodules and applied the miRNA test. Twenty-four out of 27 were positives to the test (~89%). Furthermore, the average miRNA-test risk score of the GGO group was 12.5 while the average score of two other groups of individuals with solid nodules (N=25), or without nodules (N=25), were -2.2 and -4.4 respectively (p <0.0001; Student's t-test). This confirmed the validity of the miRNA-test to predict the presence of GGO lesions as well as early stages lung cancer, and suggest that active or passive release in the blood of specific miRNA species is already present in lung premalignant lesions.

The advantages of such a test compared to ld-CT are the potential for an easy applicability on a population-wide scale, the high potential for implementation of screening on a nation-wide scale, the absence of risks related to ionizing radiations, and the reduced costs

As regards the technical aspects we have developed a fully automatized procedure based on low-density qRT-PCR array that allows the screening of expression of ~800 different miRNA species and using less than 300µl of serum. This will give us the opportunity to test every known miRNA present in the serum and to perform an accurate analysis of their quantities.

We intend to apply the very same technology to identify serum miRNAs predictive of the effect of aspirin treatment in patients with GGO lung nodules.

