## 4. PARTICIPANT SELECTION

### 4.1 Inclusion Criteria

4.1.1 Asymptomatic current or former smokers (having stopped within the last 20 years). See Appendix D

4.1.2 Age  $\geq$  50 years (risk of lung cancer in subjects under 50 is low thus screening is not indicated by actual international guidelines).

4.1.3 Smoking history  $\geq$  20 pack/years; subjects must be included in an ongoing annual screening with low dose CT scan **or**

must have two consecutive CT outside the context of a screening program confirming subsolid nodules as per inclusion criteria number 4.1.4.

4.1.4 Subjects must have subsolid (non solid or partially solid) nodules with size between 4 and 10 mm with any Volume Doubling Time (VDT) not candidate to surgical excision **and/or**

subsolid (non solid or partially solid) nodule larger than 10 mm with VDT higher than 400 days and not candidate to surgical excision.

4.1.5 All nodules should be persistent at least after three months follow up with CT; a reduction up to 15% of the diameter of the largest target nodule from the previous CT scan is allowed

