## SCHEUDLE OF EVENTS

Evaluation/ Procedure	Pre-study evaluation	Baseline Visit/Registration	Randomization	Month 1	Month 3	Month 6 visit	Month 9	Month 12 visit	Month 13	Early Termination
Informed Consent		X								
Assess pre study Eligibility (CT scan)	X									
Assess Eligibility		X								
Medical History		X								
Physical Exam/ height/weight/ vital signs		X				X		X		X
Interim medical history						X		X		X
Tobacco use assessment		X				X		X		X
Laboratory Tests		X				X		X		X
Biomarkers*§ (blood, urine)		X				X		X		
Biorepository (blood)		X						X		
CT scan					(X)¶	(X)¶		X		
Concomitant Medications	X		X	X	X	X	X	X	X	X
Baseline symptoms	X									
Dispense Study Agent			X			X				
Collect study agent						X		X		X
Compliance				X°	X°	X	X°	X		X
Review Agent Diary/Record			X			X		X		X
Adverse Events				X	X	X	X	X	X	X
Phone contact				X	X		X		X	

§Biomarkers collection at baseline, 6 and 12 month visit requires the subject to have fasted for at least 6 hours and includes TXB2 measurement; \*Blood for miRNA and urine for LTE4 and PGEM will be collected and measured at baseline and month 12 only; ° review of self reported compliance; Serum pregnancy test will be done only on potentially fertile women by β-HCG measurement; ¶ if determined to be needed during COSMOS multidisciplinary meetings

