#### *miRNA*

The effectiveness of the miRNA serum protocol will be evaluated by comparing the sensitivity, specificity and accuracy of miRNA to identify patients with GGO or with partially solid nodules and to predict aspirin treatment response considering the LDCT screening protocol as the reference procedure.

The ultimate goal is to evaluate if miRNA analysis in the serum can represent a new non-invasive test to identify patients with GGO or with partially solid nodules and to predict treatment response to low-dose aspirin.

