## 10.2 Collection and Handling Procedures

All blood and urine samples will be withdrawn under fasting condition (at least 6 hours) preferably between 8 a.m. and 10 a.m. at each time point. Instructions about specimen handling and storage will be provided in a dedicated Manual of Procedures.

A total of **8 ml** of blood will be withdrawn for safety labs (at baseline, 6 and 12 months)

A total of **4.5 ml** of blood will be collected for **miRNA** (at baseline and 12 months) with the following recommendation for each blood withdrawal:

- 1) Patients should be fasting at least 6 hours before blood collection
- 2) Information about oral therapy with anti-inflammatory, anticoagulants, steroids or other drugs will be collected the same day.
- 3) Patients must have been free of any infection (including flu) and inflammatory diseases for a week prior to the collection of blood samples.
- 4) Before any instrumental or physical examination has been performed

Fasting (at least 6 hours) blood samples will be collected in all participants free of any infection (including flu) and inflammatory diseases for a week prior to the collection of blood samples at baseline and after 12 months of treatment. In order to avoid skin contamination, the first 3 mL of blood should not be used for serum preparation. Blood samples (4.5 ml) will be collected in tubes without anti-coagulant (white cap), left at room temperature for 30-60 minutes to clot, then spun at 3000 rpm (1000 g, Megafuge 2.0 – Heraeus) for 10 minutes at room temperature. The serum will be immediately removed slowly by using a plastic transfer pipette, leaving 0.5 cm remaining to avoid disturbing the serum-clot interface, dispensed in 0.6 ml aliquots (for a total of 4 aliquots) into 1.5 ml cryotubes (Thermo Fisher Scientific), specifically labeled with a barcode, and snap frozen in dry ice. Aliquots will then be transferred in a dedicated -80°C freezer.

A total of **7.5 ml** of blood will be collected into tubes containing clot activator for **hs-CRP** (at baseline, 6 and 12 months):

Morning fasting blood samples are centrifuged at 1850xg and one ml serum aliquots will be stored into 1.5 ml cryotubes (Thermo Fisher Scientific), specifically labeled with a barcode and transferred in a dedicated -80°C freezer.

A total of **7.5 ml** of blood will be collected into tubes containing clot activator for **TXB2** (at baseline, 6 and 12 months):

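### The miRNA endpoint promises specificity and accuracy for identifying subsolid nodules, but every eligible participant has one, so at baseline specificity is 0/0 and accuracy equals sensitivity

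*Combined protocol and SAP*

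**What the plan says.** Section 8.2 (miRNA) lists as its measures "sensitivity, specificity and accuracy of miRNA to identify patients with GGO or with partially solid nodules and to predict aspirin treatment response". The same sentence then fixes the standard against which the test is judged: "considering the LDCT screening protocol as the reference procedure". Its second paragraph makes identification of patients with these nodules half of the ultimate goal; the other half is prediction of response to aspirin.

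Eligibility fixes who can be in that analysis. Under 4.1.4, "Subjects must have subsolid (non solid or partially solid) nodules with size between 4 and 10 mm", or a subsolid nodule larger than 10 mm with a volume doubling time above 400 days. Under 4.1.5, "All nodules should be persistent at least after three months follow up with CT". Section 7.1 repeats that one or more persistent subsolid nodules are needed.

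Sampling is confined to participants. The footnote to the Schedule of Events reads "Blood for miRNA and urine for LTE4 and PGEM will be collected and measured at baseline and month 12 only", and section 10.2 says "blood samples will be collected in all participants free of any infection (including flu) and inflammatory diseases".

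The biomarker rationale in section 2.3 reports earlier Cosmos 1 work on 27 people with GGO: "Twenty-four out of 27 were positives to the test". For comparison it gives mean scores in 25 people with solid nodules and 25 without nodules. Section 13.5 gives one general mixed model for secondary endpoints, by arm and visit, and section 13.10 plans no ancillary studies.

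**The concern.** Specificity is estimated only in people whom the reference standard calls negative. The eligibility criteria remove all such people, and nothing in the plan brings in others. The two groups of 25 in section 2.3 are completed work, summarised by mean score only, and no section ties them to this endpoint.

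At baseline the stated analysis would then give one undefined figure and one misleading one. An accuracy reported from this trial would look like validation of a screening test while only restating sensitivity. There is also a risk of later choice: if controls are found after the results are known, both the control group and the case-to-control mix are open, and accuracy moves with them.

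**Working it through.** **Plan's own figures.** Section 13.3 uses a difference of 0.8 mm, SD 1.6 mm, two-sided alpha 0.05 and 80% power.
- Normal approximation: n per arm = 2 × (1.960 + 0.842)² × (1.6/0.8)² ≈ 62.8, so 63.
- Exact t-test: 63.77, so 64 per arm and 128 in total, with power 0.801. The stated 128 is reproduced.
- The earlier miRNA rate is 24/27 = 0.889, matching the stated figure of about 89% (exact 95% CI 0.71 to 0.98).
- No sample size or precision is stated for the miRNA endpoint.

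**Baseline 2×2 table, 128 eligible participants.** By 4.1.4 and 4.1.5 all are reference-positive: TP + FN = 128 and TN + FP = 0.
- Sensitivity = TP/(TP + FN) = TP/128
- Specificity = TN/(TN + FP) = 0/0
- Accuracy = (TP + TN)/128 = TP/128 = sensitivity

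| Test positives | Sensitivity | Accuracy | Specificity |
|---|---|---|---|
| 64 | 0.500 | 0.500 | 0/0 |
| 114 | 0.891 | 0.891 | 0/0 |
| 128 | 1.000 | 1.000 | 0/0 |

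**What can be estimated.** Assuming the earlier rate carries over, 128 × 24/27 = 113.8, about 114. The Clopper-Pearson 95% interval for 114/128 is 0.823 to 0.939.

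**How accuracy depends on the mix.** For a test that calls everyone positive, accuracy = 128/(128 + m), where m is the number of comparators:
- m = 0: 1.00
- m = 25: 128/153 = 0.84
- m = 50: 128/178 = 0.72

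**Precision of specificity if the section 2.3 groups were used.** The documents give no specificity, so 0.80 and 0.60 are assumptions. Intervals are Clopper-Pearson 95%.

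| Assumed specificity | 25 comparators | 50 comparators |
|---|---|---|
| 0.80 | 20/25: 0.59 to 0.93 | 40/50: 0.66 to 0.90 |
| 0.60 | 15/25: 0.39 to 0.79 | 30/50: 0.45 to 0.74 |

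**Month 12.** The only negatives would be participants whose subsolid nodules had all disappeared. The documents give no rate. Assumed rates of 2%, 5% and 10% of 128 give about 3, 6 and 13 people. Even with 13, a result of 10/13 has an exact 95% interval of 0.46 to 0.95.

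**The case against.** Several points can be made for the plan.

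- **Month 12.** Section 8.2 does not confine the analysis to baseline, and miRNA is measured again at month 12. Specificity would then be defined if any participant's nodules had vanished. That is true, and the finding is limited to baseline for this reason. But those negatives would be few on any of the assumed rates, and selected by outcome and possibly by treatment. They do not measure how well the test separates people with nodules from people without.
- **Another reading.** The text might mean telling GGO from partially solid nodules. Both types are expected, since nodule type is a stratification factor in 13.2, and specificity would then exist within the trial. However, the second paragraph of the miRNA text names both types together as the condition to be found, and section 2.3 sets GGO against solid nodules or none.
- **Screening cohorts.** Section 2.3 says Cosmos 2 will validate a 34-miRNA signature, and section 9.2 relies on methods validated in Cosmos 1. The Cosmos 2 aim concerns asymptomatic lung cancer, and neither programme is linked to this endpoint. The Manual of Procedures mentioned in 10.2 was not available; it is described as covering specimen handling and storage.
- **Ineligible participants.** Section 13.8 keeps ineligible people in the response assessment, so a few without a subsolid nodule could appear. They would be enrolment errors, not a planned comparator.
- **Weight.** Identification is not among the secondary objectives in 1.2, which concern the effect of aspirin on the signature and its correlation with nodule diameter. This limits the consequence but does not make the stated analysis feasible.

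Two cautions stand. A cut-off may already exist in the cited earlier publication, though the documents do not give it. And earlier Cosmos 1 scores may not be comparable with new assay runs.

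**Conclusion.** The concern holds. At baseline there are 0 reference-negatives among 128 planned eligible participants, so specificity for identifying subsolid nodules cannot be computed and accuracy adds nothing to sensitivity. This follows from the eligibility criteria and rests on no assumed number. The assumptions enter only in the illustrations: that 24/27 carries over, and that specificity is 0.80 or 0.60.

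The effect is confined to the identification half of one secondary endpoint. Response prediction is not affected, because responders and non-responders can both occur. The primary endpoint, sample size, safety analysis and between-arm signature comparison are also untouched. It should be corrected because a stated analysis cannot be delivered and the resulting accuracy figure could be misread.

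**What to change.** Amend section 8.2 (miRNA) in one of two ways.

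**A. Narrow the claim (the simpler course).** Remove specificity and accuracy for nodule identification. Report baseline sensitivity only, with an exact 95% interval. State the positivity cut-off and fix it before the data are seen. Limit the ultimate-goal sentence to match. The cost is wording only; the downside is a narrower claim for the test.

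**B. Keep identification and supply a comparator.** Name an existing serum source from people without subsolid nodules on CT; the two groups of 25 in section 2.3 are candidates. State its size, the same pre-fixed cut-off, and whether those people were used to set it. Confirm that their scores are comparable with the trial assays. Because Cosmos 1 is also a recruitment source, check for overlap between the earlier samples and trial participants. Report specificity with its interval, and accuracy only with the case-to-control mix stated. The cost is a few sentences, with new assays if other sera are chosen or the existing scores prove not comparable. The specificity interval will be fairly wide.

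Neither option adds visits or participant samples. Response prediction and the between-arm signature comparison stay as planned.

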## 8. CRITERIA FOR EVALUATION AND ENDPOINT DEFINITION

### 8.1 Primary Endpoint

For the purposes of the primary endpoint, only sub-solid (non-solid or partially solid) nodules will be assessed. Target lesions are defined as non solid or partially solid nodules persistent at least after 3 months follow up with standard or low dose CT scan, at least 4 mm in size. Non target lesions include solid nodules (larger than 3.5 mm), new lesions at baseline (e.g., that were not present on prior CT) or non-solid or partially solid nodules < 4mm in size.

The primary end-point will be the difference in sum of longest diameters of baseline target lesions in a person-specific analysis. New subsolid lesions identified during follow-up satisfying the same criteria for the definition of target lesion will also be included in the analysis.

It has been assumed a -0.2 mm average reduction of the sum of the longest diameter of all non-solid and partially-solid lesions at 12 months with respect to baseline in the placebo arm and an expected average reduction of -1.0 mm in the aspirin group.

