## **9. CORRELATIVE/SPECIAL STUDIES**

### **9.1 Rationale for Methodology Selection**

#### Blood

##### **miRNA analysis**

miRNA extraction and purification from serum (4.5 ml of blood) will be done accordingly to standard procedure. We will analyze approximately ~850 miRNAs using the TLDA qRT-PCR microfluidic cards (Applied Biosystems) and we will determine serum miRNA relative quantities using the  $\Delta\Delta Ct$ -method. Importantly, we will check the presence of hemolysis in all serum samples collected for miRNA screening. This will be done before the miRNA extraction by visual inspection and by measuring the absorbance at 414nm^45, and after analysis of the expression ratios of couples of miRNAs found by us and by others to be sensitive enough to reveal hidden hemolysis. In addition, we will introduce spike-in synthetic miRNAs to be used as standard references in every sample screened. This will allow us to control either the efficiency of the extraction procedure and of all the qRT-PCR reactions.

Data analysis will be performed using R software (<http://www.r-project.org/>) and SAS software (<http://www.sas.com/>) for correlation analysis with all other clinical, pathological and radiological parameters.

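### Sensitivity and specificity for response, with no aspirin-versus-placebo contrast planned, cannot show that miRNA predicts benefit from aspirin

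*Combined protocol and SAP*

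**What the plan says.** Section 8.2 (miRNA) gives the endpoint two tasks, finding people with subsolid nodules and predicting who responds to aspirin, and one yardstick for both, namely sensitivity, specificity and accuracy. The second task is worded "to predict aspirin treatment response considering the LDCT screening protocol as the reference procedure". The declared goal is a non-invasive test that would also serve "to predict treatment response to low-dose aspirin". This point concerns only the second task.

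The biomarker rationale in section 2.3 words the aim in causal terms. The same assay technology will be used to "identify serum miRNAs predictive of the effect of aspirin treatment in patients with GGO lung nodules". It also describes an existing signature that was positive in 24 of 27 people with GGO nodules, and reports it as an average risk score as well. Section 9.1 plans to assay about 850 miRNAs.

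Other relevant text:
- Section 8.1 assumes that nodules shrink without aspirin too: the mean change is -0.2 mm on placebo, against -1.0 mm on aspirin.
- Section 8.2 (modified RECIST) counts shrinkage of at least 30% as success.
- Section 13.5 compares study groups on secondary endpoints in a mixed model with arm and visit as fixed effects. It does not mention miRNA and has no arm-by-marker term.
- Section 13.8 foresees no subgroup analyses.
- The schedule in section 7.1 has miRNA blood taken at baseline and month 12, with no restriction by arm.

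**The concern.** A marker can be related to shrinkage in treated people for two reasons. It may pick out nodules that tend to regress whatever is given (prognostic), or people in whom aspirin causes more shrinkage than placebo would (predictive of benefit). Only the second meets the stated goal. Sensitivity, specificity and accuracy for response measure the sum of the two. Separating them needs the same relation in the randomised placebo arm and a test of whether it differs between arms. The plan will hold those placebo data but assigns them no role in this question.

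At stake is the interpretation of one secondary endpoint. A marker of spontaneous regression could pass the stated criterion and be taken for a test that selects people for aspirin.

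**Working it through.** **1. The plan's own figures.** Section 13.3 gives a difference of 0.8 mm, SD 1.6 mm, two-sided alpha 0.05 and 80% power. The t-test solution is 63.8 per arm, so 64, with power 80.1%. This reproduces. The rationale's 24/27 = 88.9% also reproduces; its exact 95% CI is 70.8% to 97.6%.

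**2. Does placebo shrinkage produce responders?** The documents give no responder rate. As an assumption, take the change as normal with SD 1.6 mm (section 13.3) and a single nodule at the ends of the 4 to 10 mm range in criterion 4.1.4. A response is a fall of at least 30%.
- 4 mm (fall of 1.2 mm): placebo z = (-1.2 + 0.2)/1.6 = -0.625, about 27%; aspirin z = (-1.2 + 1.0)/1.6 = -0.125, about 45%.
- 10 mm (fall of 3.0 mm): placebo z = (-3.0 + 0.2)/1.6 = -1.75, about 4%; aspirin z = (-3.0 + 1.0)/1.6 = -1.25, about 11%.

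On the plan's own assumptions, a sizeable share of those who respond on aspirin would be expected to respond on placebo too.

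**3. A purely prognostic marker.** Assume response of 25% in marker-positive and 5% in marker-negative people in both arms, half positive. Aspirin then has no effect in anyone.
- Overall response: 0.5 × 0.25 + 0.5 × 0.05 = 0.15.
- Sensitivity: 0.5 × 0.25 / 0.15 = 83%.
- Specificity: 0.5 × 0.95 / 0.85 = 56%.

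Both are identical on placebo. Now let aspirin add 15 percentage points equally in both marker groups (40% and 20%), so that the marker still does not select for benefit on that scale. Sensitivity on aspirin is 0.5 × 0.40 / 0.30 = 67% and specificity 0.5 × 0.80 / 0.70 = 57%. The marker again looks informative.

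**4. Is the contrast planned elsewhere?** Sections 1.2 and 3 plan to study the effect of aspirin on the signature and to correlate marker changes with diameter changes; neither asks whether the relation differs by arm. The between-arm sentence under additional biomarkers in section 8.2 does not cover miRNA. Section 13.5 compares arms on an outcome, which is not a test of effect modification.

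**5. Conditional point on the existing signature.** If it is used at its existing cut-off, expected negatives per arm are 64 × 3/27 = 7.1. If a positive test means predicted response, and every negative is a non-responder, specificity is at most (3/27)/(1 - r): 12% at an assumed response rate r of 10%, 16% at 30%. Over the confidence interval for positivity, the ceiling runs from 0.024/0.9 = 3% to 0.292/0.7 = 42%.

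**6. What an interaction test could detect** (64 per arm, SD 1.6 mm, no dropout, normal approximation).
- Median split of a score: SE = 1.6 × √(2/32 + 2/32) = 0.57 mm. Power is 29% for an interaction of 0.8 mm; 80% power needs about 1.6 mm.
- Existing cut-off (57 and 7 per arm): SE = 1.6 × √(2/56.9 + 2/7.1) = 0.90 mm. Power is 14% for 0.8 mm; 80% power needs about 2.5 mm.
- Continuous standardised score: SE = 2 × 1.6/√128 = 0.28 mm per SD; 80% power needs about 0.79 mm per SD.

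**The case against.** The strongest reply is that the plan is less bare than it looks. Arms are compared on secondary endpoints in section 13.5, marker changes are to be correlated with diameter changes, samples come from both arms, and section 8.2 does not confine its accuracy measures to the aspirin arm. All of this is true. It shows that the data will exist, not that the needed contrast is planned. Section 8.2 is silent on arms; it does not say that only aspirin participants will be analysed.

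A reader might go further and infer that the test is useless for this purpose because about 89% of such people are positive, or that a real predictor would be hidden by a cut-off chosen to detect nodules. The documents do not support this. The 24 of 27 refers to the existing diagnostic signature in people with GGO; no rate is given for partially solid nodules. The rationale reports a score, so a yes/no cut-off is not forced. It also plans a search for other predictive miRNAs, for which no positivity rate is stated. No section says that the detection cut-off will be applied to response.

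It is also fair to say that the proposed interaction would probably be inconclusive at this sample size. That limits what the trial can claim; it does not make the accuracy measures answer the question.

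**Conclusion.** The point holds for the response-prediction half of the miRNA endpoint: no comparison of the miRNA-response relation between arms is planned, and the stated measures cannot by themselves distinguish regression from benefit. The illustration (83% and 56% with no aspirin effect) rests on assumed response rates; the logic does not depend on them.

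The 89% figure is secondary and conditional. If the existing signature is used at its existing cut-off, about 7 of 64 per arm would be negative, which leaves little room to discriminate. This does not carry over to a newly derived predictor or to the continuous score. Nor do the documents say that a prognostic marker will be reported as predicting benefit; they only leave nothing in place to prevent it.

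The change should be made, but it concerns one secondary endpoint. The primary analysis and safety are untouched.

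**What to change.** In section 8.2 (miRNA), replace the response-prediction metric with one regression using both arms: 12-month change in the sum of longest diameters on arm, a prespecified continuous baseline miRNA score, and their interaction. Add the model to section 13.5, which at present has no miRNA analysis. Specifically:
- Fix the score before unblinding. Section 6.9 leaves the statistician unblinded, so also document it before miRNA results are linked to outcomes.
- Report the interaction with its 95% CI, labelled exploratory, and name it in section 13.8 as an exception to the statement on subgroup analyses.
- Report sensitivity and specificity for response separately by arm, as description only.
- Treat any predictor newly selected from the roughly 850 miRNAs as hypothesis-generating, since no validation or multiplicity rule is given for that search.

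The cost is protocol wording; samples, assays and visits do not change. The drawback is the low precision shown above, about 29% power for a 0.8 mm interaction with a median split, so a wide interval must not be read as absence of effect modification.
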